8.4.4 Pregnancy

Women of childbearing potential are excluded from participation in this study.

8.5 Other assessments

8.5.1 Immunogenicity

IG samples will be collected at the time points defined in the assessment schedule. All samples will be given a unique sample number as indicated in the log that is included in the MOP. Further details on sample collection, numbering, processing and shipment can be found in the MOP.

Validated immunoassays are used for the detection of anti-CLG561 and anti-LFG316 antibodies.

Corporate Confidential Information

8.5.2 Pharmacokinetics

PK samples must be collected at the time points defined in the assessment schedule.

All samples are given a unique sample number as indicated in the log that is included in the MOP. Further details on sample collection, numbering, processing and shipment can be found in the MOP. Total CLG561 and total LFG316 is determined by a validated immunoassay method. A detailed description of the methods used to quantify the concentration of total CLG561 and total LFG316 will be included in the bioanalytical raw data of the study and in the bioanalytical data report. The LLOQ will be documented in the bioanalytical data reports.

Samples from the sham group is not analyzed for total CLG561 or total LFG316. Concentrations below the LLOQ is reported as “zero” and missing data is labeled as such in the Bioanalytical Data Report.

Corporate Confidential Information

8.5.3 Drug administration

IVT or Sham Injections will be administered as described in the assessment schedule and in the MOP.

Novartis

Confidential

Page 71

Amended Protocol Version No. 01 (Clean)

Protocol No. CCLG561X2201A

8.5.4 Ocular examination

In addition to ocular efficacy endpoint assessments, the following must be conducted as part of the ocular examination:

- Best Corrected Visual Acuity
- Low Luminance Visual Acuity
- Intraocular Pressure
- Slit-lamp Biomicroscopy
- Dilated Ophthalmoscopy (Dilated Fundus Exam)

Immediately post-injection, gross visual acuity must be performed.

Corporate Confidential Information

8.5.8 General comments

The Investigator may record general comments as deemed necessary in the source and eCRF to document important and scientifically notable details throughout the trial.

Novartis

Confidential

Page 72

Amended Protocol Version No. 01 (Clean)

Protocol No. CCLG561X2201A

Corporate Confidential Information

Novartis

Confidential

Page 73

Amended Protocol Version No. 01 (Clean)

Protocol No. CCLG561X2201A

Corporate Confidential Information

Protocol No. CCLG561X2201A

9 Safety monitoring

9.1 Adverse events - general information

An AE is any untoward medical occurrence in a subject who is administered a study treatment regardless of whether or not the event has a causal relationship with the treatment. An AE, therefore, can be any unfavorable or unintended sign (including an abnormal laboratory finding), symptom, or disease temporally associated with the study treatment, whether or not related to the treatment. In clinical studies, an AE can include an untoward medical occurrence occurring at any time, including run-in or washout periods, even if no study treatment has been administered. The determination of clinical relevance is based upon the medical judgment of the Investigator.

9.2 Monitoring for adverse events

At each visit, after the subject has had the opportunity to spontaneously mention any problems, the Investigator should inquire about AEs by asking the standard questions:

- “Have you had any health problems since your last study visit?”
- “Have there been any changes in the medicines you take since your last study visit?”

AEs must be reported for any clinically relevant change in concomitant medication(s) that is the result of an untoward (unfavorable and unintended) change in a subject's medical health.

Changes in any protocol-specific parameters and questionnaires (if applicable) evaluated during the study are to be reviewed by the Investigator. Any untoward (unfavorable and unintended) change in a protocol-specific parameter or questionnaire response that is clinically relevant is to be reported as an AE. These clinically relevant changes will be reported regardless of causality.

9.3 Procedures for recording and reporting AEs and SAEs

Subsequent to signing an informed consent form, all untoward medical occurrences that occur during the course of the study must be documented on an Adverse Event Form (AEF). A separate AEF must be filled out for each event. When possible, signs and symptoms indicating a common underlying pathology must be documented as one comprehensive event. For each recorded event, the AE documentation must include the onset date, outcome, resolution date (if event is resolved), intensity (e.g., severity), any action with study treatment taken as a result of the event, and an assessment of the AE's relationship to the study

Novartis

Confidential

Page 74

Amended Protocol Version No. 01 (Clean)

Protocol No. CCLG561X2201A

Once an AE is detected, it must be followed until its resolution or until it is judged to be permanent, and assessment must be made at each visit (or more frequently, if necessary) of any changes in severity, the suspected relationship to the study drug, the interventions required to treat it, and the outcome.

Information about common side effects that are already known about the investigational drug can be found in the IB or Core Data Sheet (for marketed drugs) or will be communicated between IB updates in the form of Investigator Notifications. This information will be included in the subject informed consent and must be discussed with the subject during the study as needed.

The Investigator should also instruct each subject to report any new AE (beyond the protocol observation period) that the subject, or the subject's personal physician, believes might reasonably be related to study treatment. This information must be recorded in the Investigator's source documents; however, if the AE meets the criteria of an SAE, it must be reported to Sponsor.

Non-serious Adverse Events

A non-serious AE is defined as any untoward change in a subject's medical health that does not meet serious criteria noted below (e.g., is not life-threatening, does not require hospitalization, does not prolong a current hospitalization, is not disabling, etc.). All AEs must be reported regardless of whether or not they are related to the study treatment. For non-serious AEs, an AEF containing all available information will be collected on a routine basis according to instructions provided by the study sponsor.

Serious Adverse Events

A SAE is defined as any adverse experience that meets any of the following criteria:

- Results in death
- Is life-threatening
- Note: Life-threatening means that the subject was at immediate risk of death from the reaction as it occurred, i.e., it does not include a reaction which hypothetically might have caused death had it occurred in a more severe form
- Requires hospitalization or prolongation of existing hospitalization

Note: In general, hospitalization signifies that the individual remained at the hospital or emergency ward for observation and/or treatment (usually involving an overnight stay) that would not have been appropriate in the physician's office or an out-subject setting. Complications that occur during hospitalization are AEs. If a complication prolongs hospitalization or fulfills any other serious criteria, the event is serious. When in doubt as to whether "hospitalization" occurred, the event must be considered serious.

- Results in persistent or significant disability/incapacity. Disability is defined as a substantial disruption of a person's ability to conduct normal life functions
Note: The term disability means a substantial disruption of a person's ability to conduct normal life functions. This definition is not intended to include experiences of relatively minor medical significance such as uncomplicated headache, nausea, vomiting, diarrhea, influenza, or accidental trauma (e.g., sprained ankle) which may interfere or prevent everyday life functions but do not constitute a substantial disruption
- Is a congenital anomaly/birth defect
- Is an important medical event. An important medical event is an event that may not result in death, be life- threatening, or require hospitalization but may be considered an SAE when, based upon appropriate medical judgment, it may jeopardize the subject and may require medical or surgical intervention to prevent one of the outcomes listed in the definitions for SAEs. Examples of such medical events include allergic bronchospasm requiring intensive treatment in an emergency room or at home, blood dyscrasias or convulsions that do not result in a subject's hospitalization, or the development of drug dependency or drug abuse

All available information on a SAE(s) must be forwarded to the study Sponsor immediately (i.e., within 24 hours of the Investigator's or site's knowledge of the event) as follows:

- In studies utilizing EDC (electronic data capture), all available information for the SAE must be entered immediately into the EDC system. Note: Should the Electronic Data Capture (EDC) system become non-operational, the site must complete the appropriate paper SAE Form. The completed form is faxed to the study Sponsor at [name] within 24 hours of the Investigator's or site's awareness; however, the reported information must be entered into the EDC system once it becomes operational.
- Sponsor representatives and their contact information are provided in the MOP that accompanies this protocol.
- Additional information for any applicable event is to be reported as soon as it becomes available.

In addition to the reporting of SAEs to the study sponsor, the SAE must be reported to the IRB / IEC according to their requirements.

If the SAE was due to a hospitalization of the subject, a copy of the discharge summary is to be forwarded to the study Sponsor as soon as it becomes available. In addition, a letter from the Investigator that summarizes the events related to the case as well as results of any relevant laboratory tests also may be requested. Further, depending upon the nature of the SAE, the Sponsor may request copies of applicable portions of the subject's medical records.

An assessment of seriousness will also be performed for all AEs by a study Sponsor physician utilizing the same criteria. If an AE reported for an Investigator's subject is upgraded to a SAE by a study Sponsor physician, the Investigator will receive a notification by the study Sponsor.

Adverse Events of Special Interest

An AE of special interest is one of scientific and medical concern specific to the sponsor's product, route of administration or program where ongoing monitoring and rapid communication by the Investigator to the sponsor may be appropriate. These AEs may be serious or non-serious. Applicable AEs may require further investigation in order to characterize and understand, and depending upon the nature of the event, rapid communication by the trial sponsor to other parties may also be required. These AEs of special interest must be reported using the same mechanism (EDC or fax) and timeframe (i.e., within 24 hours of the Investigator's or site's knowledge of the event) as described previously for SAEs.

The AEs of special interest include the following:

- Endophthalmitis
- Grade ≥ 3 aqueous flare and/or Grade 4 aqueous cells (see MOP for grading scale)
- Grade 2 aqueous flare and/or Grade 2 or 3 aqueous cells that fail to decrease to 1 or less within 30 days of the onset of the event (see MOP for grading scale)
- Grade ≥ 2 vitreous haze and/or Grade ≥ 3 vitreous cells (see MOP for grading scale)
- ≥ 30 letter decrease in BCVA compared with Baseline visual acuity
- Sustained (> 15 minutes) loss of light perception due to elevated IOP
- IOP > 30 mmHg at/past 60 minutes post injection
- New retinal tear or detachment
- New vitreous hemorrhage $> 2+$ severity that does not resolve within 30 days of the onset of the event (see MOP for grading scale)

If an ESI occurs in a study subject, a decision will be made by the Sponsor concerning further exposure to study treatment. The study subject will be followed for resolution of the ESI and a decision will be made by the Sponsor concerning further participation in the study.

9.4 Intensity and causality assessments

For every AE, the Investigator must assess the intensity (severity) and causality (relationship to study treatment). Specifically, events must be classified as mild, moderate, or severe. The assessment of causality will be based upon the categories of related and not related. These classifications must be based on the following definitions:

Intensity (Severity)

- | | |
|----------|---|
| Mild | An event is mild if the subject is aware of, but can easily tolerate the sign or symptom. |
| Moderate | An event is moderate if the sign or symptom results in discomfort significant enough to cause interference with the subject's usual activities. |
| Severe | An event is severe if the sign or symptom is incapacitating and results in the subject's inability to work or engage in their usual activities. |

Novartis

Confidential

Page 77

Amended Protocol Version No. 01 (Clean)

Protocol No. CCLG561X2201A

Causality

Related AEs classified as related may be either definitely related or possibly related where a direct cause and effect relationship between the study treatment and the event has not been demonstrated but there is a reasonable possibility that the event was caused by the study treatment.

Not Related AEs classified as not related may either be definitely unrelated or simply unlikely to be related (i.e., there are other more likely causes for the AE).

An assessment of causality will also be performed by a study sponsor physician utilizing the same definitions. For a serious AE reported by an Investigator as not related that upon review of the available data by the study sponsor physician is assessed (upgraded) to be related, the Investigator will receive a notification.

9.5 Unmasking of study treatment

Not applicable; this study is single masked (subject masked).

9.6 Follow-up of subjects with adverse events

The Investigator is responsible for adequate and safe medical care of subjects during the trial and for ensuring that appropriate medical care and relevant follow-up procedures are maintained after the trial. Any additional data from these follow-up procedures must be documented and available to the Sponsor who will determine when the data need to be documented on the case report forms.

Pregnancy reporting

Women of childbearing potential are defined as all women physiologically capable of becoming pregnant. Women of childbearing potential are excluded from this study.

Pregnancy is not reportable as an AE; however, complications may be reportable and will be decided on a case by case basis. A Sponsor specific pregnancy form is utilized to capture all pregnancy-related information until birth of the child or termination of pregnancy.

10 Data review and database management

10.1 Site monitoring

Before study initiation, the Sponsor representative will review the protocol and other study documentation with the Investigators and their staff. Training may occur at a site initiation visit or at an Investigator's meeting.

During the study Sponsor employs several methods of ensuring protocol compliance, GCP compliance, and the quality and integrity of the sites' data. The Clinical Site Manager (CSM) will visit the site to review:

- Completeness of subject records
- Accuracy of entries on the eCRFs
- Adherence to the protocol and to Good Clinical Practice
- Progress of enrollment
- Ensure that study drug is being stored, dispensed, and accounted for according to specifications

Key study personnel must be available to assist the CSM during the study monitoring visits.

Continuous remote monitoring of each site's data may be performed by the Sponsor. A central analytics team may analyze data, identify risks, identify trends for site operational parameters, and provide reports to Sponsor Clinical Teams to assist with trial oversight.

The nature and location of all source documents will be identified to ensure that original data required to complete the eCRFs exist and are accessible for verification by the site manager. If electronic records are maintained, the method of verification must be determined in advance of starting the study. The Investigator must maintain source documents for each subject in the study. Source documents consist of case and visit notes (e.g. hospital or clinic medical records) that may include demographic and medical information, laboratory data, and the results of any other tests or assessments. All information on eCRFs must be traceable to the source documents. It is required that all entries in the source documents are identified by the author. The Investigator must also keep the original informed consent form signed by the subject. The Investigator must provide a signed copy to the subject.

The Investigator must give the clinical site manager access to all relevant source documents to confirm their consistency with the eCRF entries. Sponsor monitoring standards require full verification for the presence of informed consent, adherence to the eligibility criteria, documentation of SAEs, and the recording of data that is used for all primary and safety variables. Additional checks of the consistency of the source data with the eCRFs are performed according to the study-specific monitoring plan. No information in source documents about the identity of the subjects, beyond subject number and demographic information, is disclosed.

Novartis

Confidential

Page 79

Amended Protocol Version No. 01 (Clean)

Protocol No. CCLG561X2201A

10.2 Data collection

The EDC uses fully validated software that conforms to 21 CFR Part 11 requirements. Designated Investigator site staff are required to enter the data specified by the protocol into the eCRFs. Designated Investigator site staff must not be given access to the EDC system until they have been trained.

The Investigator must certify that the data entered into the eCRFs are complete and accurate. After database lock, the Investigator will receive electronic files of the subject data for archiving at the investigational site.

All data captured for this study will have an external originating source (either written or electronic) with the eCRF not considered as source.

All data must be recorded, handled and stored in a way that allows its accurate reporting, interpretation and verification.

Sponsor staff will review the data entered into the eCRFs by investigational staff for completeness and accuracy. Sponsor staff may instruct the site personnel to make required corrections or additions. Queries are sent to the investigational site using an electronic data query. Designated Investigator site staff are required to respond to the query and confirm or correct the data.

Concomitant medications entered into the database are coded using the WHO Drug Reference List, which employs the Anatomical Therapeutic Chemical classification system. Medical history/current medical conditions and AEs will be coded using the MedDRA terminology.

Laboratory samples are processed centrally or at an external laboratory. The results are sent electronically to the Sponsor.

The Interactive Response Technology (IRT) is used to:

- Store randomization codes
- Store data in reference to dispensing of study products to the subject

The system is supplied by a vendor that manages the IRT database. The IRT database is sent electronically to the Sponsor.

The occurrence of any protocol deviations must be determined prior to database lock. Once the database is declared to be complete and accurate, it is locked and the data becomes available for data analysis. Any changes to the database after that database lock can only be made by joint written agreement between the Global Head of Clinical Information Sciences and the Clinical Franchise Head.

Corporate Confidential Information

10.3 Data monitoring committee

Not required.

10.4 Adjudication committee

Not required.

10.5 Safety committee

The study team, consisting of Investigators and a Sponsor internal clinical team, MUST provide rigorous AE monitoring oversight of each individual subject following their first dose, and prior to their second and third doses. If the number or severity of drug-related AEs are of concern, the safety committee may put a treatment arm or the whole study on hold until further review of the available safety data.

10.6 Regulatory documentation and records retention

The Investigator is required to maintain updated and complete regulatory documentation. The Investigator's files are reviewed as part of ongoing study monitoring. Financial information is not subject to regulatory inspection and MUST be kept separately.

Additionally, the Investigator MUST keep study records and source documents until the Sponsor provides written approval for their destruction. IF the Investigator retires, relocates, or withdraws from responsibility of the study records, THEN study record custody MUST be transferred to the Sponsor or a designee.

11 Data analysis

11.1 Analysis sets

The final subject evaluability will be determined prior to locking the database.

The full analysis set will be used for assessment of efficacy and the data from both the study eye and fellow eye (fellow eye as reference for the within subject comparison) will be used for analysis. The full analysis set will include all subjects who receive any study treatment and have at least one follow-up visit with an assessment of the GA lesion size. The full analysis set will use the treatment as randomized.

The per-protocol (PP) set will be used for assessment of efficacy and the data from both the study eye and fellow eye will be used for analysis. The PP set will be comprised of all full analysis set subjects who have no critical protocol deviations, and have a valid assessment of the primary efficacy endpoint (change in geographic atrophy lesion size from baseline to Day 337 as assessed by FAF). Key per protocol criteria are compliance regarding the monthly injection schedule up to Day 337 (not missing greater than 1 in any 6 months period or not missing 2 consecutive doses) and in addition to baseline lesion size assessment the corresponding assessment on Day 337 and/or Day 253. Protocol deviations will be identified and classified before database lock. The PP analysis set will use the treatment as randomized. The PP set is the primary efficacy analysis set.

Novartis

Confidential

Page 81

Amended Protocol Version No. 01 (Clean)

Protocol No. CCLG561X2201A

The safety analysis set will include all subjects that received any study drug.

The PK analysis set will include all subjects with available PK data and no protocol deviations with relevant impact on PK data.

The PD analysis set will include all subjects with available PD data and no protocol deviations with relevant impact on PD data.

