2.2 Secondary objective(s)

Objective	Endpoint

 To evaluate the time course of the change in GA lesion size of the active arms as compared to sham as measured by FAF in the study eye 	
 Change in GA lesion size from baseline to Day 85, 169, 253, and 421 as measured by FAF in the study eye

 To evaluate the time course of the change in BCVA/low luminance visual acuity/low luminance visual acuity deficit up to Day 337 of the active arms as compared to sham in the study eye 	
 Change in BCVA/low luminance visual acuity/low luminance visual acuity deficit from baseline by visit up to Day 337 as measured by ETDRS in the study eye

 To evaluate the average change in BCVA/low luminance visual acuity/low luminance visual acuity deficit from baseline to the period Day 281 to Day 337 of the active arms as compared to sham in the study eye 	
 Average change in BCVA/low luminance visual acuity/low luminance visual acuity deficit from baseline to the period Day 281 to Day 337 as measured by ETDRS in the study eye

 To evaluate the time course of the proportion of study eyes losing or gaining ≥ 15 letters, ≥ 10 letters, and ≥ 5 letters in BCVA from baseline up to Day 337 in each of the active arms as compared to sham in the study eye 	
 Subject status regarding ≥ 15 letters, ≥ 10 letters, and ≥ 5 letters change from baseline in BCVA by visit up to Day 337 as measured by ETDRS in the study eye

 To describe: 
 The systemic exposure of total CLG561 after IVT administration of CLG561 as a monotherapy up to Day 421 The systemic exposure of total CLG561 and total LFG316 after IVT administration of CLG561 in combination with LFG316 up to Day 421 	
 Serum concentrations of total CLG561 (CLG561 monotherapy) and serum concentrations of total CLG561 and total LFG316 (CLG561/LFG316 combination) by visit up to Day 421

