CCLG561X2201A	Screen	Treatment Period																		EOS ⁶	
		N/A	V1	V2	V3	V4	V5	V6	V7	V8	V9	V10	V11	V12	V13	V14	V15	V16	V17		
Visit Numbers ¹	-30 to -1	BL/D1	D2	D8	D15	D29	D30	D57	D85	D113	D141	D169	D197	D225	D253	D281	D309	D337	D421		
Day	-30 to -1	BL/D1	D2	D8	D15	D29	D30	D57	D85	D113	D141	D169	D197	D225	D253	D281	D309	D337	D421		
CLG561 and LFG316 concentration sample collection		X ³	X	X	X	X ³				X ³			X ³		X ³		X ³	X	X		
Corporate Confidential Information																					
IG sample collection			X ³				X ³			X ³			X ³		X ³		X ³	X	X		
Corporate Confidential Information																					

¹ Visit structure is given for internal programming purposes only

² Body temperature, blood pressure, and pulse rate must be measured prior to IVT injection

³

Corporate Confidential Information

Unscheduled visit assessments as needed and as determined by the investigator

Corporate Confidential Information

Table 8-2 Ocular assessments

CCLG561X2201A	Screen	Treatment Phase																FU	EOS ¹⁰
		N/A	V1	V2	V3	V4	V5	V6	V7	V8	V9	V10	V11	V12	V13	V14	V15	V16	
Visit Number	N/A																		V18 (V777)
Day	-30 to -1	BL / D1	D2	D8	D15	D29	D30	D57	D85	D113	D141	D169	D197	D225	D253	D281	D309	D337	D421
Visit Window (Days)			+/- 1	+/- 1	+/- 1	-2	+ 1	+/- 5	+/- 5	+/- 5	+/- 5	+/- 5	+/- 5	+/- 5	+/- 5	+/- 5	+/- 5	+/- 5	+/- 7
Injection		1				2		3	4	5	6	7	8	9	10	11	12		
Ocular examination ^{1,2,3}																			
Best corrected visual acuity	OU	OU	OU	OU	OU	OU	OU	OU	OU	OU	OU	OU	OU	OU	OU	OU	OU	OU	
Low luminance visual acuity		OU	OU			OU	OU	OU	OU	OU	OU	OU	OU	OU	OU	OU	OU	OU	
Intraocular pressure	OU	OU ⁴	SE	SE	SE	SE ⁴	SE	SE ⁴	SE										
Slit lamp biomicroscopy	OU	OU	SE	SE	SE	SE	SE	SE	SE	SE	SE	SE	SE	SE	SE	SE	SE	OU	
Dilated ophthalmoscopy	OU	OU ⁵	SE	SE	SE	SE ⁵	SE	SE ⁵	SE	OU									

Corporate Confidential Information

Color fundus photo	OU	OU								OU			OU			OU	OU	OU
Fundus autofluorescence	OU	OU								OU			OU			OU	OU	OU
Fluorescein angiography	OU																	OU

Corporate Confidential Information

Novartis
 Amended Protocol Version No. 01 (Clean)

Confidential

Page 64
 Protocol No. CCLG561X2201A

Visit Number	Screen	Treatment Phase															FU	EOS ¹⁰		
		N/A	V1	V2	V3	V4	V5	V6	V7	V8	V9	V10	V11	V12	V13	V14	V15	V16		
Day	-30 to -1	BL / D1	D2	D8	D15	D29	D30	D57	D85	D113	D141	D169	D197	D225	D253	D281	D309	D337	D421	V18 (V777)

Corporate Confidential Information

All ocular examinations may be performed at the physician's discretion

² OU: both eyes

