11.5 Analysis of secondary and exploratory variables

11.5.1 Efficacy endpoints

Analyses will be performed for both the PP set and the FAS.

Potential treatment effects will primarily be assessed based on the difference in change from baseline in the study eye between active treatment and sham treatment. In addition, the corresponding difference between study and fellow eye will be explored within the active treatment arms.

At time points assessed, each efficacy endpoint will be presented graphically and by descriptive statistics provided for observed absolute values and changes from baseline. Changes from baseline will be compared between treatment arms using ANOVA models and/or stratified/unstratified Cochran-Mantel-Haenszel Tests.

Corporate Confidential Information

For treatment differences and differences between study and fellow eye 80% confidence intervals will be provided.

The following secondary endpoints will be evaluated:

- Change in geographic atrophy lesion size from baseline to Days 85, 169, 253, 337 and 421 as measured by fundus auto-fluorescence
- Change in BCVA, low luminance visual acuity and low luminance visual acuity deficit from baseline by visit up to Day 337 as measured by ETDRS in the overall population and in subsets of patients with baseline visual acuity < 73 letters
- Subject status regarding ≥ 15 letters, ≥ 10 letters, and ≥ 5 letters change from baseline in BCVA by visit up to Day 337
- Average change in BCVA/low luminance visual acuity/low luminance visual acuity deficit from baseline to the period Day 281 to Day 337

For the changes in geographic atrophy lesion size from baseline between either of the active arms and sham as measured by FAF, the same analysis model used for the primary hypothesis (Section 11.4.2) will be used.

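### The full analysis set requires a follow-up GA lesion assessment but is also used for visual acuity, so some early leavers with valid acuity data drop out of the early acuity comparisons (minor)

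*Protocol*

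**What the plan says.** Protocol Section 11.1 admits to the FAS subjects "who receive any study treatment and have at least one follow-up visit with an assessment of the GA lesion size". The set is not reserved for lesion endpoints: "The full analysis set will be used for assessment of efficacy". The PP set inherits the condition, since "The PP set will be comprised of all full analysis set subjects who have no critical protocol deviations", and it adds dosing compliance and a lesion assessment at Day 253 and/or Day 337.

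For the secondary efficacy endpoints, Section 11.5.1 states: "Analyses will be performed for both the PP set and the FAS". Its list includes "Change in BCVA, low luminance visual acuity and low luminance visual acuity deficit from baseline by visit up to Day 337" and "Subject status regarding ≥ 15 letters, ≥ 10 letters, and ≥ 5 letters change from baseline in BCVA by visit up to Day 337". No separate acuity set is defined.

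On timing, the row "Best corrected visual acuity" in Table 8-2 is filled at every visit from Day 2. The follow-up lesion endpoint in Section 2.2 starts later: "Change in GA lesion size from baseline to Day 85, 169, 253, and 421 as measured by FAF in the study eye".

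**The concern.** Membership of the set is decided by one endpoint and then applied to others that are measured sooner. Whether a Day 2 to Day 57 acuity value counts depends on whether the subject later supplies a lesion assessment. That is selection on an event after randomisation, and it discards values already collected.

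What is at stake is the planned between-arm comparison of acuity at the visits before Day 85, for which Section 11.5.1 provides treatment differences with 80% confidence intervals. With about 38 subjects per arm, one or two exclusions can change a letter-change proportion noticeably. Treatment differs visibly between arms and the investigators are not masked (Sections 3.1 and 3.2), so early departure could differ by arm.

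**Working it through.** **1. The plan's own numbers.** Inputs from Section 11.6: difference 0.67 mm², SD 1.2 mm², one-sided alpha 0.1, power 80%, drop-out/protocol deviation rate 20%.

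- Normal approximation: n = 2 × 1.2² × (1.2816 + 0.8416)² / 0.67² = 28.9, so 29 per arm.
- Noncentral t: power is 0.796 at 29 and 0.807 at 30, so 30 per arm is right.
- Inflation: 30 / 0.80 = 37.5, so 38 per arm and 3 × 38 = 114.

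The stated 30, 38 and 114 reproduce. The point here does not touch them.

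**2. Order of assessments.**

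- Post-baseline BCVA before Day 85 (Table 8-2): Days 2, 8, 15, 29, 30 and 57, which is six visits.
- First scheduled follow-up lesion size (Section 2.2): Day 85.

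The count of six is for BCVA. The low luminance row of Table 8-2 is not legible enough in the available text to count its early visits.

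**3. Who is excluded.** A subject must have at least one post-baseline acuity value, leave before Day 85, and have no lesion assessment at an end-of-study (EOS) visit. Section 3.1 asks early leavers to return for an EOS visit with all assessments. Under Section 7.3, no further assessments follow withdrawal of consent, and subjects lost to follow-up (Section 7.2.1) do not attend. These are the main routes.

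**4. How many.** The documents give no figure, so this rests on assumptions: drop-out rate d, uniform over 337 days, with a fraction f of early leavers lacking an EOS lesion assessment.

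Expected number = 114 × d × (85/337) × f, with 85/337 = 0.252.

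| d | f = 0.25 | f = 0.5 | f = 1 |
|---|---|---|---|
| 5% | 0.4 | 0.7 | 1.4 |
| 10% | 0.7 | 1.4 | 2.9 |
| 20% | 1.4 | 2.9 | 5.8 |

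The range is about 0 to 6 of 114, at most about 5%. The upper end treats the whole 20% as drop-out, although Section 11.6 gives it as drop-out and protocol deviation together, and assumes that nobody attends an EOS visit.

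**5. What a few exclusions can do.** Six spread evenly is 2 per arm. If both had lost at least 15 letters and nobody else in that arm had, the reported proportion at that visit would be 0/36 = 0% instead of 2/38 = 5.3%. With one such subject it would be 0/37 = 0% instead of 1/38 = 2.6%. This is an illustration, and it applies equally to an active arm or to sham.

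**6. What is not exposed.** A subject who leaves before Day 85 has no acuity values in the Day 281 to 337 window and adds little or nothing to later by-visit comparisons. The primary lesion analysis uses the PP set.

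**The case against.** The strongest reply is that the protocol already closes most of the gap. Early leavers are to have a full EOS evaluation (Section 3.1). Stopping treatment is not in itself withdrawal from the study (Section 7.1), so such subjects can still reach Day 85. Subjects discontinued because the study eye needed other intravitreal treatment are also to have the follow-up visit and EOS evaluation (Sections 5.2 and 6.9). BCVA is summarised by treatment group and visit under safety (Section 11.5.6), and a loss of 30 letters or more is an event of special interest reported within 24 hours (Section 9.3). The affected results are secondary, in a proof-of-concept study. All of this stands and limits the size. It does not remove the mismatch, because consent withdrawal and loss to follow-up remain, and the descriptive safety summaries of change from Screening do not replace the planned comparison with sham of change from baseline.

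A reader might infer two stronger things.

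- **That an ungradable study-eye image removes the subject.** Section 11.1 names no eye, autofluorescence imaging is done in both eyes, and one assessment at any follow-up visit is enough. Even if only the study eye counted, every follow-up image would have to fail.
- **That the exclusion favours active treatment because only those arms receive a needle.** The mechanism can be imagined, but the documents give no counts of early leavers by arm and nothing on their acuity. The direction is not established.

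**Conclusion.** The point holds as a minor one. A stated membership rule, tied to a follow-up assessment of a different endpoint, drops subjects with valid acuity data from the acuity comparisons at the visits before Day 85. The number is unknown: about 0 to 6 of 114 under the assumption of uniform drop-out, and possibly none. The exclusion could differ by arm, in a direction that cannot be read from the documents. The primary PP lesion analysis, the sample size, the Day 281 to 337 acuity average and the safety reporting of BCVA are essentially unaffected.

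**What to change.** In Section 11.1, define the FAS as all randomised subjects who received at least one study or sham injection, analysed as randomised. Add that each FAS efficacy endpoint is analysed in subjects with a baseline and at least one post-baseline value of that same endpoint in the study eye. Naming the eye also settles what the present wording leaves open.

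The FAS lesion-size analyses keep essentially the same subjects, and the FAS acuity analyses regain data already collected. The PP set is unchanged, so the PP acuity analyses stay as restricted as they are now. The cost is a sentence or two, with no new data, visits or subjects. The one drawback is that n will differ slightly between the lesion and acuity tables.
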